Title: Adductor Canal Mid-thigh and Adductor Canal Distal Thigh: Is Cutaneous Sensory Blockade Similar Among Block Techniques?

NCT02788019

Document Date: 05/06/2016 (Date IRB officially approved)

**The University of Texas Southwestern Medical Center at Dallas
Institutional Review Board**

Protocol (for Investigator Initiated Studies)

Title: Adductor Canal Mid-thigh and Adductor Canal Distal Thigh: Is Cutaneous Sensory Blockade Similar Among Block Techniques?

Principal Investigator: [name].

Co-Investigators:

[name].

[name].

[name].

[name].

[name].

[name]

Funding Source: UT Southwestern Department of Anesthesiology and Pain Management.

1. Introduction and Purpose:

The adductor canal block (ACB), or the “sub-sartorial mid-thigh” or “distal thigh saphenous block”, are relatively new approaches in which local anesthetic is deposited within an aponeurotic tunnel in the middle-third of thigh containing multiple nerves.¹⁻⁵ ACB is predominately a blockade of multiple sensory nerves block with limited motor involvement. The block is utilized for knee surgery and for medial blockade of the leg (i.e., at or below the knee).⁶⁻⁹

The primary nerves located in this area are the saphenous nerve and a single efferent motor nerve, which is the distal branch of the femoral nerve that innervates the vastus medialis of the quadriceps muscle. In the distal portion of the adductor canal, a sensory branch of the posterior obturator nerve often enters the canal.^{10,11} It is unclear if other nerves are found regularly in this anatomic location though it has been suggested that the medial femoral cutaneous nerve and medial retinacular nerve may be among them.⁹ Debate is ongoing within the regional anesthesia literature regarding anatomy, differences of block technique and their potential effects on block results.¹²⁻¹⁵ While comparisons of block technique have been studied,^{16,17} there are no published studies regarding cutaneous sensation in light of the newly defined block technique parameters, to our knowledge.^{10,12-14,18} We seek to confirm that the areas of sensory blockade are the same or differ following the two different types of adductor canal block in the area that is proximal to the knee. This knowledge can help improve patient analgesia and lower postsurgical opioid consumption for future patients having surgery in this area.

Hypothesis 1: The area of sensory blockade is different as a result of blockade at the mid-thigh and distal locations for the adductor canal block.

Specific Aim 1: To assess if the difference in cutaneous sensation to pinprick at 20-minutes after the block in patients randomized to receive mid-thigh or distal-thigh adductor canal blockades.

Hypothesis 2: To reconfirm that the mid-thigh and distal-thigh approaches to the ACB provide similar postoperative pain control for medial leg, medial ankle and medial foot surgery.

Specific Aim 2: To evaluate differences in the postoperative verbal response score in two randomized groups of patients received mid-thigh and distal-thigh adductor canal blockade in the first 24 hours postoperative.

Hypothesis 3: The maximum voluntary isometric contraction (MVIC) generated for knee extension is similar following the mid-thigh and distal thigh approaches to the ACB.

Specific Aim 3: To test the MVIC of knee extension with a hand held dynamometer at 20 minutes after the mid-thigh and distal-thigh approaches to the ACB.

Hypothesis 4: There is no difference in block performance time and patient satisfaction of two ACB techniques.

Specific Aim 4. To evaluate the differences in block performance time and patient satisfaction for two different ACB techniques.

Primary Endpoint:

- Distribution of cutaneous sensation to pinprick at 20-minutes and 30-minutes after the block.

Secondary Endpoints:

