Eligible and interested females of childbearing age will have a urine pregnancy test the morning of surgery. Exceptions include surgically sterile women or women with medically confirmed menopause. Urine (5 ml) will be collected for the urine pregnancy test (UPT). This is the routine clinical practice at Clements University Hospital, Zale Lipshy Hospital and the Outpatient Surgical Center as a part of the pre-procedure standard of care. Any females with a positive UPT will be excluded from the study.

Following the discussion and UPT (if necessary), informed written consent for clinical care and participation in the study will be obtained.

Once a patient is enrolled, they will be randomized to one of two groups, mid-thigh ACB or distal ACB, using a computer generated randomization program. The site will be marked, and a time out will be performed. A grid will be marked starting with anatomical landmarks at the knee joint: the medial inter-knee-joint point where the tibia meets the femur, the mid medial patella, the mid lateral patella, and along the same line at the semitendinosus tendon and 5cm posterior from that point. Then 5cm intervals will be plotted progressing cephalad to a total of 15 centimeters. This will yield 20 grid points.

The distribution of baseline sensation will be evaluated at the grid and documented. The degree of sensory block will be evaluated over the grid area with Neuropen prick testing on a scale of 0-1, with 1 = normal sharp sensation, 0 = change of sensation. The Neuropen will be used for the standardization of force.¹⁹⁻²¹ The primary outcome will be the number of grid-points with a change in sensation at 20 minutes and 30 minutes after the block. The second post block measurement is to ensure that the block is effective, as this will vary with each patient, and there is potential to miss important sensory change if measurement is taken too early. The current clinical guidelines list a block onset time between 15-30 minutes.

MVIC of the ipsilateral quadriceps muscle will be assessed using a handheld dynamometer and recorded.²²⁻²⁵

Patients will receive a preoperative ultrasound-guided single-injection ACB at either the mid-thigh or distal approach according to their randomization and according to the technique descriptions provided in the Background section of this protocol and consistent with standard UTSW peripheral nerve block procedures.

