Billing should be in accordance with standard practice and not paid for by the study, as all procedures are deemed standard of care. Patients will not be reimbursed for participation of the research.

Recorded Measures:

1. Baseline number of grid-points with full sensation.
2. The number of grid-points with a change in sensation at 20-minutes after the block to determine distribution of cutaneous sensory blockade.
3. Baseline ipsilateral quadriceps MVIC: 3 measurements of 5 seconds each separated by 30 seconds while seated with hip and knee at 90 degrees
4. MVIC at 20 minutes and 30 minutes as tested with same method as baseline test
5. Block performance time (needle in skin until needle out of skin)
6. Patient satisfaction for postoperative pain management
7. Pain scores on a 0-10 Likert scale at PACU (1-h) and at postoperative Day 1 (POD1) approximately 24 h following to surgery (0=no pain, 10=worse imaginary pain)
8. For inpatients, all recorded pain scores in the first 24 hours
9. Opioid consumption in PACU and for first 24 h

PHI including name, date of birth, MRN number, contact information including phone number will be recorded. Demographic information such as age, height, weight, BMI, race/ethnicity, and gender will be recorded. Medical and surgical history including allergies, pre-existing condition such diabetes, and medication list, ASA classification, type of anesthesia, laboratory results, regional anesthesia techniques, sensory mapping for adductor canal block, postoperative pain management, postoperative pain scores, and type of surgery will also be recorded.

4. Study Procedures:

- Potential subjects will be identified at the orthopedic presurgical clinic, the anesthesia preoperative clinic or the Day Surgery Unit. The electronic medical record (Epic) will also be used for prescreening potential subjects.
- Recruitment and consenting at Anesthesia preoperative clinics, Day Surgery Unit.
- Randomization: A computer generated randomization list will be used for randomization list.
 - **Anatomical landmarks at the knee joint:**

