 - Sensory blockade will be assessed over a grid area. The grid will be marked starting with anatomical landmarks at the knee joint: the medial inter-knee-joint point where the tibia meets the femur, the mid medial patella, the mid lateral patella, and along the same line at the semitendinosus tendon and 5cm posterior from that point. Then 5cm intervals will be plotted progressing cephalad to a total of 15 centimeters. This yields 20 grid points.
 - The study will use a 20 point-grid to standardize evaluation of sensory blockade in the anticipated border zone of block distribution. It will take approximately 1-2 minutes to make the grid and perform the testing. This is specifically for research purposes.
 - **Pinprick testing:**
 - The Sensory block for sharp sensations will be assessed by using Pinprick testing. Pinprick testing will be tested on a scale of 0-1, with 1 = normal sharp sensation and 0 = dull change of sensation, using a Neuropen for standardization of force.¹⁹⁻²¹
 - Sensation to the Neuropen will be performed gently across the skin with the end of the device to assess sharp touch. The subject will be asked to determine whether the stimulus feels sharp. The number of grid-points with a change in sensation from baseline will be recorded at 20-minutes and 30-minutes after the block.
 - Mechanical stimulation with pinprick testing is routinely used to test nociception in the bedside neurologic examination. Sharpness can be considered a surrogate for nociception because, whereas sharpness is not necessarily painful, mechanical thresholds for sharpness closely parallel those for pain.²⁶
 - **Maximum Voluntary Isometric Contraction:**
 - The MVIC will be assessed with a handheld dynamometer (Lafayette Instrument Company; Lafayette, Indiana).

- The patient will be in a seated position with the thigh parallel to the floor and the knee at a 90-degree angle with the feet off the floor. The dynamometer is applied to the leg 5 cm above the transmalleolar axis and perpendicular to the tibial crest. The patient is instructed to extend the leg at the knee with sustained maximal force for 5 seconds. This will be repeated 3 times with 30 seconds rest between each movement, and the force will be recorded. MVIC will be assessed at baseline and again at 20 minutes and 30 minutes post block.
 - **Adductor Canal Blockade:**

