Stored electronic data that contains PHI and/or other types of identifiable data will be encrypted and password protected and stored on a secure server. Subject identifiers will not be reused or disclosed to any other person or entity for research unless required by law, for authorized conduct and oversight of the study, or for other IRB-approved research.

All protected health information will be kept in a secure location with limited access.

Following the completion of the analysis and the project, the key to the coding system will be destroyed by shredding the documents so that there is no direct or indirect link to subject identifiers and information.

13. Potential Benefits:

Potential benefits in determining whether the two neurosensory blockade techniques are different include identifying a potential difference in the area of sensory blockade of the thigh, a potential difference in strength as indicated by MVIC, as well as suggesting a potential improvement in analgesia of the thigh and subsequent increase in patient satisfaction, as well as decreased postoperative opioid usage for future patients.

Both neurosensory blockade techniques are very safe, have little or no pain associated with administration, and have the same cost.

14. Biostatistics:

Sample Size Estimation:

There is no prior study to provide basis for a sample size estimation. Thus the study is powered to achieve 70% power with two-sided alpha = 0.05 for testing the equivalence of the two blocking methods. With an equivalence margin of 2 points (two blocking methods will be equivalent if mean score for one blocking method within two points of the other) and assuming a standard deviation of 3 points, the study will have 70% power with n = 34 in each group (total n = 68).

Statistical analyses:

Data will be summarized as mean and standard deviation for continuous variables and frequency and percentages for categorical variables. The equivalence of the two blocking methods will be tested using the two-one-sided-tests (TOST) procedure following Schuirmann (1987).²⁸ Pain scores and opiate consumption will also be analyzed in subgroups according to the location and type of surgery (foot vs. ankle vs. leg) and presence of concurrent sciatic block.

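### The primary endpoint is named distribution, but the outcome and the equivalence rule use only a count of blocked grid points, which measures extent and not location

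*Combined protocol and SAP*

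**What the plan says.** Section 1 (Introduction and Purpose) sets out to learn whether the blocked territories "are the same or differ following the two different types of adductor canal block in the area that is proximal to the knee". Under Primary Endpoint it lists "Distribution of cutaneous sensation to pinprick at 20-minutes and 30-minutes after the block". Hypothesis 1 reads: "The area of sensory blockade is different as a result of blockade at the mid-thigh and distal locations for the adductor canal block".

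Section 3 (Concise Summary of Project) gives the working definition: "The primary outcome will be the number of grid-points with a change in sensation at 20 minutes and 30 minutes after the block". Each point is scored 0 or 1. Recorded Measures item 2 ties the count to the endpoint's name: "The number of grid-points with a change in sensation at 20-minutes after the block to determine distribution of cutaneous sensory blockade". Section 4 (Study Procedures) explains why the grid is used: "The study will use a 20 point-grid to standardize evaluation of sensory blockade in the anticipated border zone of block distribution".

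Section 14 (Biostatistics) sets a 2-point margin and an SD of 3 points, with 34 patients per group and a TOST. Its decision rule is "two blocking methods will be equivalent if mean score for one blocking method within two points of the other". It does not define the score.

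Location does appear in the plan. Sensory mapping is secondary endpoint 5 in section 1, a recorded item in section 3 and a listed source of research material in section 8. Section 14 also provides for frequencies and percentages of categorical variables.

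**The concern.** The plan says that a count determines a distribution, and it cannot. Two patients with 6 of 20 points blocked may share all six points or none. The count measures the extent of block within the grid. It therefore suits Hypothesis 1 if area means size, but it does not deliver the endpoint as named.

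Location is a live question here because the arms differ by injection site. On the distal level, section 1 notes: "In the distal portion of the adductor canal, a sensory branch of the posterior obturator nerve often enters the canal". If the TOST passes, the result will stand under the heading of distribution, next to a stated purpose of learning whether the areas are the same. The trial would then invite a conclusion about territory from data on extent. Section 14 neither plans a between-arm comparison of location nor says that the equivalence conclusion leaves location out.

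**Working it through.** **Inputs.** From section 14: margin 2, SD 3, 34 per arm, target power 70%, alpha 0.05. From section 3: 20 points, each scored 0/1. One reading is ours: the undefined score is the grid-point count, the only primary outcome the plan defines.

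**1. The plan's own figure.**
- The standard error of the difference is 3 × √(2/34) = 0.728, and margin/SE = 2/0.728 = 2.749.
- With 0.05 per one-sided test and a true difference of 0, the normal approximation to the power is 2Φ(2.749 − 1.645) − 1 = 0.730.
- The exact t-based calculation, integrating over the pooled variance, gives 0.718. The smallest n per group that reaches 70% is 34, so the sample size is reproduced.
- At 0.025 per test the power would be 0.546 and 42 per group would be needed. The plan's figure therefore implies 0.05 per test.

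**2. Why location drops out.** Let b(i,j) = 1 if point j is blocked in patient i. The outcome is K(i) = Σ b(i,j) over the 20 points. The TOST uses only the arm means and the pooled SD of K. Relabelling the points in one arm moves that arm's territory anywhere on the grid and leaves every K(i) unchanged, so the TOST result is the same. The pass rate of 71.8% at equal means and SD 3 thus holds for coinciding, partly overlapping and disjoint territories alike.

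An assumed extreme shows this. One block affects only one half of the grid (10 points) and the other block only the other half, each with mean count 5 and SD 3 (beta-binomial), 34 per arm. Equivalence was declared in 71.9% of 20,000 simulated trials.

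**3. What the count can see.** Added territory raises the mean count. For a true difference d, the approximate power is Φ((2 − d)/0.728 − 1.645) + Φ((2 + d)/0.728 − 1.645) − 1. The exact values are:

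| True difference in mean count | TOST pass rate, 34 per arm | 17 per arm |
|---|---|---|
| 0 | 71.8% | 21.2% |
| 1.0 | 38.1% | 13.6% |
| 2.0 | 5.0% | 3.6% |

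The 17-per-arm column applies if the trial stops at 34 patients, as section 14 allows, with equal allocation. Extra skin numbed by one block alone is therefore partly visible. The blind spot is confined to territories that differ while the mean counts stay similar.

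**4. What per-point data could show.** The approximate 95% half-width for a difference in proportions is 1.96 × √(2p(1 − p)/n).
- 34 per arm: 0.24 at p = 0.5 and 0.14 at p = 0.1.
- 17 per arm: 0.34 and 0.20.

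**5. Multiplicity if points are to be declared different.** Identical blocks were simulated with 20 correlated points, Newcombe intervals and 34 per arm, at assumed rates of 0.6 on 8 points and 0.1 on 12. At least one of the 20 intervals at 95% excluded 0 in 53–59% of trials. Other assumed rate patterns gave 17–68%. Bonferroni over one time point (99.75%) brought this to 5% or less at that time. Over both times together it still reached about 9–11% in simulation. Covering 20 × 2 = 40 comparisons needs 1 − 0.05/40 = 99.875%, which gave about 4%.

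**The case against.** The strongest reply is that nobody would be misled about what to test. Sections 3 and 4 all define the outcome as a number of points, and the rule in section 14 is expressly about a mean score. No passage says that a passed TOST shows the same skin is blocked. Location is also planned for: mapping is a secondary endpoint, and percentages per point are within the general summary rule. The study calls itself a pilot. Both techniques target the saphenous nerve in the adductor canal, so disjoint territories are an artificial extreme.

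Much of this stands, and it rules out three stronger readings that a reader might infer:

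- **That the plan ignores location.** It does not. What is missing is a between-arm comparison of location.
- **That 72% is the chance of a false claim of same territory.** It is the pass rate at equal mean counts, and any test of a mean count behaves this way. The documents give no expected overlap, so the likelihood of displaced territories is unknown.
- **That the sample size or the test is wrong.** The 34 per group is reproduced, and the count is a valid measure of extent.

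What the reply does not remove is the inference written in Recorded Measures item 2, that the count determines distribution, and the same word as the name of the primary endpoint. A secondary endpoint without a stated comparison does not correct that. Nor does pilot status, since this pilot has a formal equivalence decision and a stopping rule attached to it.

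**Conclusion.** The concern holds in a limited form, and the text is wrong as written: a count of changed points does not determine their distribution. A passed TOST would support equivalence in the mean extent of block within the grid. It would be no evidence that the two approaches numb the same skin. The defect lies in the endpoint's name and in what may be concluded, not in the arithmetic. Its practical weight depends on how often territories differ at similar counts, which the documents do not tell us.

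The conclusion rests on reading the section 14 score as the grid-point count. The figures also rest on the plan's SD of 3 and on 0.05 per one-sided test. The change is worth making because it alters what the trial can claim, at almost no cost.

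**What to change.** Keep the 68 patients, the count and the TOST.

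1. **Section 1, Primary Endpoint.** Rename it: *Number of grid points (of 20) with a change in pinprick sensation at 20 and 30 minutes after the block (extent of block within the grid).* In Recorded Measures item 2 (section 3), replace the closing purpose clause with *to determine the extent of cutaneous sensory blockade within the grid*. That item gives 20 minutes only; align it with the 20 and 30 minutes in the Primary Endpoint, the primary outcome in section 3 and the pinprick procedure in section 4.

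2. **Section 14, after the TOST sentence.** Add: *The TOST conclusion is equivalence in the mean number of blocked grid points only, not in their location.*

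3. **Section 14, for the sensory-mapping endpoint.** Add: *The 20 results per patient and time point are kept. The proportion blocked at each point is reported by arm at 20 and 30 minutes, with the between-arm difference and its 95% Newcombe CI, as description only. No point is declared different from these intervals, and a CI that includes 0 is not read as the same territory.*

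If the sponsor wants to declare individual points different, that is an exploratory test. It should be labelled so and use 99.875% Newcombe intervals (Bonferroni over 20 points at two times). The interval method must be named because it matters. At assumed rates of 0.6 and 0.1 with 17 per arm, a 99.75% interval excludes 0 in about 53% of trials by Newcombe and 72% by Wald.

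**Cost.** There are no extra patients or measurements, since every point is already scored 0/1. The equivalence claim becomes narrower and the per-point intervals are wide. Large differences at a point can be described, but small differences, or sameness of territory, will rarely be shown.

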1. MVIC
2. Post-operative Pain scores, stratify to type of surgery
3. Opioid consumption
4. Block performance time
5. Characterization of cutaneous sensory block area by sensory mapping
6. Patient satisfaction

2. Background:

The adductor canal block is used for surgical anesthesia and/or postoperative pain control for surgeries involving the medial foot, medial ankle or medial leg. Different investigators have described varying techniques in accomplishing the adductor canal block as detailed here:

Manickam (distal thigh adductor canal): “The leg...was externally rotated, the knee slightly flexed. The medial aspect of the thigh was scanned in a transverse axial plane using a high-frequency linear probe prepared in a sterile fashion. The saphenous nerve was identified in a cross-sectional (short axis) view as it runs alongside the femoral artery in the adductor canal deep to the sartorius muscle. The transducer was initially placed on the medial aspect of the distal third of the thigh to identify the femoral artery immediately deep to the sartorius muscle. The transducer was then moved caudally along the long axis of the thigh until the femoral artery was seen “diving” deep and moving away from the anterior muscle plane (sartorius and vastus medialis muscles), toward the posterior aspect of the thigh where it becomes the popliteal artery. This area was identified as the “adductor hiatus,” and the block location was selected 2 to 3 cm proximally to this area, in the distal adductor canal...The nerve was identified as a slightly hyperechoic structure with a round cross-section, in close relationship to the femoral artery, usually slightly superficial to it.”¹

Lund/Jaeger/Machi: mid-thigh adductor canal “A high-frequency linear ultrasound transducer was placed transverse to the longitudinal axis of the extremity at the mid-thigh level at a distance approximately halfway between the iliac spine and the patella. The femoral artery was identified underneath the sartorius muscle with the vein just underneath the artery. At this position, the saphenous nerve was placed lateral to the artery in the adductor canal. A 10cm Tuohy...was inserted, in plane, from the lateral side of the transducer, through the sartorius muscle with the tip placed lateral to the artery.”⁵

“The midpoint between the anterior superior iliac spine and the cephalad margin of the patella was measured with slight external rotation of the leg at the hip. Using ultrasound at this midpoint, the superficial femoral artery was identified in a short-axis view deep to the sartorius muscle, medial to the rectus femoris muscle and anterior to the adductor longis muscle, with the superficial femoral vein usually posterolateral to the artery. At this position, the ultrasound image of the saphenous nerve or nerve bundle is typically anterolateral to the superficial femoral artery within the adductor canal. The corresponding anatomical positions for each structure are saphenous nerve anterior to the artery, vein lateral to the artery, and sartorius medial to the artery...the final needle tip positioning between the artery and the saphenous nerve. If the saphenous nerve could not be well visualized, the needle tip was placed at 5 o’clock relative to the femoral artery within the adductor canal.”⁸

3. Concise Summary of Project:

This investigation will be a randomized interventional prospective pilot study. Patients undergoing medial foot, medial ankle, or medial leg surgery (n= 68) will be randomized to evaluate two types of adductor canal blocks. Patients will be identified during their orthopedic presurgical clinic visit, anesthesia preoperative clinic visit or Day Surgery Unit (Zale Lipshy Hospital, Clements University Hospital, UTSW Outpatient Surgery Center) for the eligibility. The electronic medical record (Epic) will also be used for prescreening of potential study participants by reviewing the clinic visit daily schedule or operating room schedule. Then patient charts will be reviewed for initial data collection to determine the eligibility of potential subjects with the use of a HIPAA waiver form. Eligible individuals may be introduced to the study in the orthopedic presurgical clinic or the anesthesia preoperative

clinic by staff. Those individuals interested in participation will then be contacted to learn about the study by study personnel.

A discussion of risks, benefits and alternatives will be performed.

Eligible and interested females of childbearing age will have a urine pregnancy test the morning of surgery. Exceptions include surgically sterile women or women with medically confirmed menopause. Urine (5 ml) will be collected for the urine pregnancy test (UPT). This is the routine clinical practice at Clements University Hospital, Zale Lipshy Hospital and the Outpatient Surgical Center as a part of the pre-procedure standard of care. Any females with a positive UPT will be excluded from the study.

Following the discussion and UPT (if necessary), informed written consent for clinical care and participation in the study will be obtained.

Once a patient is enrolled, they will be randomized to one of two groups, mid-thigh ACB or distal ACB, using a computer generated randomization program. The site will be marked, and a time out will be performed. A grid will be marked starting with anatomical landmarks at the knee joint: the medial inter-knee-joint point where the tibia meets the femur, the mid medial patella, the mid lateral patella, and along the same line at the semitendinosus tendon and 5cm posterior from that point. Then 5cm intervals will be plotted progressing cephalad to a total of 15 centimeters. This will yield 20 grid points.

The distribution of baseline sensation will be evaluated at the grid and documented. The degree of sensory block will be evaluated over the grid area with Neuropen prick testing on a scale of 0-1, with 1 = normal sharp sensation, 0 = change of sensation. The Neuropen will be used for the standardization of force.¹⁹⁻²¹ The primary outcome will be the number of grid-points with a change in sensation at 20 minutes and 30 minutes after the block. The second post block measurement is to ensure that the block is effective, as this will vary with each patient, and there is potential to miss important sensory change if measurement is taken too early. The current clinical guidelines list a block onset time between 15-30 minutes.

MVIC of the ipsilateral quadriceps muscle will be assessed using a handheld dynamometer and recorded.²²⁻²⁵

Patients will receive a preoperative ultrasound-guided single-injection ACB at either the mid-thigh or distal approach according to their randomization and according to the technique descriptions provided in the Background section of this protocol and consistent with standard UTSW peripheral nerve block procedures.

A research assistant who is blinded to ACB approach will record the time taken to perform the block as defined as the time from the start of local anesthetic infiltration of the skin to the time the block needle was removed from the patient (Block performance time).

At the end of block performance a stopwatch will be started. Pinprick sensation and MVIC will occur at 20 minutes after block completion.

The efficacy of postoperative analgesia will be evaluated by using a 0-10 Likert scale (0=no pain, 10= worst imaginable pain). Pain will be evaluated in the PACU within 1 h postoperatively and postoperative Day 1 (POD1). If the patient is discharged to home, a phone interview will be performed within 24 h following the surgery for evaluation of POD1 pain scores, patient satisfaction, and monitoring adverse events.

Patient satisfaction as a measure of quality of pain management will be assessed POD1 via phone call on the scale of 1 to 5 (Poor=1, Fair=2, Good=3 Very good=4, Excellent=5).

The duration of the study period is 24 hours. Although participants will be participating in a research protocol, their clinical care will be the standard of care as if they were not involved in a research protocol (i.e. both types of blocks are performed routinely in clinical practice at Clements University Hospital and Zale Lipshy Hospital). As such, adjunct pain control using multimodal analgesia will be used to achieve adequate pain control. Preoperative gabapentin, acetaminophen or opiate medications as well as intraoperative opiates, ketamine, alpha-2-agonists, NSAID, acetaminophen or other analgesic may be used according to the standard of care multimodal analgesia practice. Postoperative adjuvant analgesics may include but is not limited to acetaminophen, NSAID, gabapentin, oral and IV opiate as needed, as well as opiate by IV patient controlled analgesia. For some types of surgery, concurrent sciatic nerve block may be desired and performed according to the anesthetic plan devised by the patient's faculty anesthesiologist in collaboration with the attending surgeon and patient wishes. To ensure appropriate completion of study protocol, the adductor canal block and all study procedures would occur before the sciatic block, which would still occur before surgery as is the standard of care. Those individuals who receive a sciatic block would have pain analyzed in a separate group from those receiving only an adductor canal block.

Billing should be in accordance with standard practice and not paid for by the study, as all procedures are deemed standard of care. Patients will not be reimbursed for participation of the research.

Recorded Measures:

1. Baseline number of grid-points with full sensation.
2. The number of grid-points with a change in sensation at 20-minutes after the block to determine distribution of cutaneous sensory blockade.
3. Baseline ipsilateral quadriceps MVIC: 3 measurements of 5 seconds each separated by 30 seconds while seated with hip and knee at 90 degrees
4. MVIC at 20 minutes and 30 minutes as tested with same method as baseline test
5. Block performance time (needle in skin until needle out of skin)
6. Patient satisfaction for postoperative pain management
7. Pain scores on a 0-10 Likert scale at PACU (1-h) and at postoperative Day 1 (POD1) approximately 24 h following to surgery (0=no pain, 10=worse imaginary pain)
8. For inpatients, all recorded pain scores in the first 24 hours
9. Opioid consumption in PACU and for first 24 h

PHI including name, date of birth, MRN number, contact information including phone number will be recorded. Demographic information such as age, height, weight, BMI, race/ethnicity, and gender will be recorded. Medical and surgical history including allergies, pre-existing condition such diabetes, and medication list, ASA classification, type of anesthesia, laboratory results, regional anesthesia techniques, sensory mapping for adductor canal block, postoperative pain management, postoperative pain scores, and type of surgery will also be recorded.

4. Study Procedures:

- Potential subjects will be identified at the orthopedic presurgical clinic, the anesthesia preoperative clinic or the Day Surgery Unit. The electronic medical record (Epic) will also be used for prescreening potential subjects.
- Recruitment and consenting at Anesthesia preoperative clinics, Day Surgery Unit.
- Randomization: A computer generated randomization list will be used for randomization list.
 - **Anatomical landmarks at the knee joint:**
 - Sensory blockade will be assessed over a grid area. The grid will be marked starting with anatomical landmarks at the knee joint: the medial inter-knee-joint point where the tibia meets the femur, the mid medial patella, the mid lateral patella, and along the same line at the semitendinosus tendon and 5cm posterior from that point. Then 5cm intervals will be plotted progressing cephalad to a total of 15 centimeters. This yields 20 grid points.
 - The study will use a 20 point-grid to standardize evaluation of sensory blockade in the anticipated border zone of block distribution. It will take approximately 1-2 minutes to make the grid and perform the testing. This is specifically for research purposes.
 - **Pinprick testing:**
 - The Sensory block for sharp sensations will be assessed by using Pinprick testing. Pinprick testing will be tested on a scale of 0-1, with 1 = normal sharp sensation and 0 = dull change of sensation, using a Neuropen for standardization of force.¹⁹⁻²¹
 - Sensation to the Neuropen will be performed gently across the skin with the end of the device to assess sharp touch. The subject will be asked to determine whether the stimulus feels sharp. The number of grid-points with a change in sensation from baseline will be recorded at 20-minutes and 30-minutes after the block.
 - Mechanical stimulation with pinprick testing is routinely used to test nociception in the bedside neurologic examination. Sharpness can be considered a surrogate for nociception because, whereas sharpness is not necessarily painful, mechanical thresholds for sharpness closely parallel those for pain.²⁶
 - **Maximum Voluntary Isometric Contraction:**
 - The MVIC will be assessed with a handheld dynamometer (Lafayette Instrument Company; Lafayette, Indiana).

- The patient will be in a seated position with the thigh parallel to the floor and the knee at a 90-degree angle with the feet off the floor. The dynamometer is applied to the leg 5 cm above the transmalleolar axis and perpendicular to the tibial crest. The patient is instructed to extend the leg at the knee with sustained maximal force for 5 seconds. This will be repeated 3 times with 30 seconds rest between each movement, and the force will be recorded. MVIC will be assessed at baseline and again at 20 minutes and 30 minutes post block.
 - **Adductor Canal Blockade:**
- The adductor canal block will be performed using a linear HFL38xp or a linear HFL38x ultrasound probe (X-Porte or M-Turbo; SonoSite; Bothell, Washington). The site that is to receive the ACB will be sterilized with chlorhexidine gluconate 2% and 70% isopropyl alcohol prep. A skin wheal of lidocaine 1% (2-5mL) will be delivered. A Tuohy needle (17 gauges) will be inserted through the skin wheal under ultrasound guidance towards the target nerve location. Ropivacaine 0.5% 15ml will be injected for either adductor canal locations.²⁷
- The research intervention of this study will take place within the standard clinical context. The patient will receive an ACB regardless of their participation in this research in accordance with their anesthetic plan and their desires.
- **Follow-up visit:**
- A follow-up visit will be performed in person for inpatients or via phone for outpatients within 24 hours from discharge to assess for pain control, and monitoring side effects. It will take 10 minutes.
- **Monitoring Adverse Events**
- Adverse events will be monitored during the 24-h study period.

5. Sub-Study Procedures:

N/A

6. Criteria for Inclusion of Subjects:

1. Adult patients age \geq 18 years
2. Individuals undergoing surgery of the medial foot, medial ankle, medial leg or knee for which the anesthetic plan includes an adductor canal nerve block

Selection for inclusion will not be based on gender, race, or socioeconomic status. The study population of interest includes men and women of all races and socioeconomic status. There will be no participants from vulnerable populations, such as pregnant women, children or prisoners.

Patients can decline enrollment. If they do so, they will still receive a peripheral nerve block for postoperative analgesia according to the plan determined by the anesthesia provider at the time of service in accordance with the patient's wishes.

7. Criteria for Exclusion of Subjects:

1. Any known deficit of the ipsilateral lumbar nerve roots, ipsilateral lumbar plexus, ipsilateral femoral nerve, obturator nerve or saphenous nerve including diabetic peripheral neuropathy
2. Any local disorder of the skin or otherwise where blockade is to be performed
3. Body mass index >50
4. ASA classification greater than 3
5. Allergy to amide local anesthetic medications
6. Pregnancy
7. Incarceration
8. Inability to understand study procedures including inability to understand the English language

8. Sources of Research Material:

